- **Time Course:** Did the AE follow in a reasonable temporal sequence from administration of the Sponsor's product? Is the time of onset of the AE compatible with a drug-induced effect (applies to trials with investigational medicinal product)?
- **Likely Cause:** Is the AE not reasonably explained by another etiology such as underlying disease, other drug(s)/vaccine(s), or other host or environmental factors
- **Dechallenge:** Was the Sponsor's product discontinued or dose/exposure/frequency reduced?
 - If yes, did the AE resolve or improve?
 - If yes, this is a positive dechallenge.
 - If no, this is a negative dechallenge.

(Note: This criterion is not applicable if: (1) the AE resulted in death or permanent disability; (2) the AE resolved/improved despite continuation of the Sponsor's product; (3) the trial is a single-dose drug trial); or (4) Sponsor's product(s) is/are only used one time.)

- **Rechallenge:** Was the participant re-exposed to the Sponsor's product in this trial?
 - If yes, did the AE recur or worsen?
 - If yes, this is a positive rechallenge.
 - If no, this is a negative rechallenge.

(Note: This criterion is not applicable if: (1) the initial AE resulted in death or permanent disability, or (2) the trial is a single-dose drug trial); or (3) Sponsor's product(s) is/are used only one time.)

NOTE: IF A RECHALLENGE IS PLANNED FOR AN ADVERSE EVENT WHICH WAS SERIOUS AND WHICH MAY HAVE BEEN CAUSED BY THE SPONSOR'S PRODUCT, OR IF RE-EXPOSURE TO THE SPONSOR'S PRODUCT POSES ADDITIONAL POTENTIAL SIGNIFICANT RISK TO THE PARTICIPANT THEN THE RECHALLENGE MUST BE APPROVED IN ADVANCE BY THE SPONSOR CLINICAL DIRECTOR AS PER DOSE MODIFICATION GUIDELINES IN THE PROTOCOL, AND IF REQUIRED, THE INSTITUTIONAL REVIEW BOARD/INDEPENDENT ETHICS COMMITTEE.

- **Consistency with Study treatment Profile:** Is the clinical/pathological presentation of the AE consistent with previous knowledge regarding the Sponsor's product or drug class pharmacology or toxicology?
- The assessment of relationship will be reported on the case report forms /worksheets by an investigator who is a qualified physician according to his/her best clinical judgment, including consideration of the above elements.

- Use the following scale of criteria as guidance (not all criteria must be present to be indicative of a Sponsor's product relationship).
 - Yes, there is a reasonable possibility of Sponsor's product relationship: There is evidence of exposure to the Sponsor's product. The temporal sequence of the AE onset relative to the administration of the Sponsor's product is reasonable. The AE is more likely explained by the Sponsor's product than by another cause.
 - No, there is not a reasonable possibility of Sponsor's product relationship: Participant did not receive the Sponsor's product OR temporal sequence of the AE onset relative to administration of the Sponsor's product is not reasonable OR the AE is more likely explained by another cause than the Sponsor's product. (Also entered for a participant with overdose without an associated AE.)
- For each AE/SAE, the investigator must document in the medical notes that he/she has reviewed the AE/SAE and has provided an assessment of causality.
- There may be situations in which an SAE has occurred and the investigator has minimal information to include in the initial report to the Sponsor. However, it is very important that the investigator always make an assessment of causality for every event before the initial transmission of the SAE data to the Sponsor.
- The investigator may change his/her opinion of causality in light of follow-up information and send an SAE follow-up report with the updated causality assessment.
- The causality assessment is one of the criteria used when determining regulatory reporting requirements
- For studies in which multiple agents are administered as part of a combination regimen, the investigator may attribute each adverse event causality to the combination regimen or to a single agent of the combination. In general, causality attribution should be assigned to the combination regimen (i.e., to all agents in the regimen). However, causality attribution may be assigned to a single agent if in the investigator's opinion, there is sufficient data to support full attribution of the adverse event to the single agent.

Follow-up of AE and SAE

- The investigator is obligated to perform or arrange for the conduct of supplemental measurements and/or evaluations as medically indicated or as requested by Sponsor to elucidate the nature and/or causality of the AE or SAE as fully as possible. This may include additional laboratory tests or investigations, histopathological examinations, or consultation with other health care professionals.
- New or updated information will be recorded in the CRF.
- The investigator will submit any updated SAE data to the Sponsor within 24 hours of receipt of the information.

Reporting of AE, SAE, and Other Reportable Safety Events to the Sponsor

AE, SAE, and Other Reportable Safety Event Reporting to Sponsor via Electronic Data Collection Tool

• The primary mechanism for reporting to the Sponsor will be the electronic data collection (EDC) tool.• Electronic reporting procedures can be found in the EDC data entry guidelines (or equivalent).• If the electronic system is unavailable for more than 24 hours, then the site will use the paper AE Reporting form.• Reference section 9.3.1 – Time Period and Frequency for Collecting AE and SAE and Other Reportable Safety Event Information for reporting time requirements• The site will enter the SAE data into the electronic system as soon as it becomes available.• After the study is completed at a given site, the electronic data collection tool will be taken off-line to prevent the entry of new data or changes to existing data.• If a site receives a report of a new SAE from a study participant or receives updated data on a previously reported SAE after the electronic data collection tool has been taken off-line, then the site can report this information on a paper SAE form or by telephone (see next section).• Contacts for SAE reporting can be found in the Investigator Trial File Binder (or equivalent).
SAE Reporting to the Sponsor via Paper CRF

• If the electronic data collection tool is not operational, facsimile transmission or secure e-mail of the SAE paper CRF is the preferred method to transmit this information to the Sponsor.• In rare circumstances and in the absence of facsimile equipment, notification by telephone is acceptable with a copy of the SAE data collection tool sent by overnight mail or courier service.• Initial notification via telephone does not replace the need for the investigator to complete and sign the SAE CRF pages within the designated reporting time frames.• Contacts and instructions for SAE reporting and paper reporting procedures can be found in the Investigator Trial File Binder (or equivalent).

12.6 Appendix 6: Contraceptive Guidance and Pregnancy Testing

Woman of Childbearing Potential (WOCBP)

A woman is considered fertile following menarche and until becoming post-menopausal unless permanently sterile (see below)

Women in the following categories are not considered WOCBP:

- Premenarchal
- Premenopausal female with 1 of the following:
 - Documented hysterectomy
 - Documented bilateral salpingectomy
 - Documented bilateral oophorectomy

Note: Documentation can come from the site personnel's review of the participant's medical records, medical examination, or medical history interview.

- Postmenopausal female
 - A postmenopausal state is defined as no menses for 12 months without an alternative medical cause.
 - A high follicle stimulating hormone (FSH) level in the postmenopausal range may be used to confirm a postmenopausal state in women not using hormonal contraception or hormonal replacement therapy (HRT). However, in the absence of 12 months of amenorrhea, confirmation with two FSH measurements in the postmenopausal range is required.
 - Females on HRT and whose menopausal status is in doubt will be required to use one of the non-hormonal highly effective contraception methods if they wish to continue their HRT during the study. Otherwise, they must discontinue HRT to allow confirmation of postmenopausal status before study enrollment.

Contraception Requirements

Male Participants:

Male participants with female partners of childbearing potential are eligible to participate if they agree to one of the following during the protocol defined time frame in section 6.1:

- Be abstinent from penile-vaginal intercourse as their usual and preferred lifestyle (abstinent on a long term and persistent basis) and agree to remain abstinent
- Use a male condom plus partner use of a contraceptive method with a failure rate of <1% per year as described in [Table 14](#) when having penile-vaginal intercourse with a woman of childbearing potential who is not currently pregnant.
 - Note: Men with a pregnant or breastfeeding partner must agree to remain abstinent from penile-vaginal intercourse or use a male condom during each episode of penile penetration.

Female Participants:

Female participants of childbearing potential are eligible to participate if they agree to use one of the contraception methods described in [Table 14](#) consistently and correctly during the protocol-defined time frame in Section 6.1.

Table 14 Contraceptive Methods

Acceptable Contraceptive Methods Failure rate of >1% per year when used consistently and correctly.

• Male or female condom with or without spermicide• Cervical cap, diaphragm or sponge with spermicide
Highly Effective Contraceptive Methods That Are User Dependent ^a Failure rate of <1% per year when used consistently and correctly.

• Combined (estrogen- and progestogen- containing) hormonal contraception^b
◦ Oral◦ Intravaginal◦ Transdermal◦ Injectable• Progestogen-only hormonal contraception^b
◦ Oral◦ Injectable
Highly Effective Methods That Have Low User Dependency Failure rate of <1% per year when used consistently and correctly.

• Progestogen- only contraceptive implant ^{b, c}• Intrauterine hormone-releasing system (IUS) ^b• Intrauterine device (IUD)• Bilateral tubal occlusion
• Vasectomized partner
A vasectomized partner is a highly effective contraception method provided that the partner is the sole male sexual partner of the WOCBP and the absence of sperm has been confirmed. If not, an additional highly effective method of contraception should be used.
• Sexual abstinence
Sexual abstinence is considered a highly effective method only if defined as refraining from heterosexual intercourse during the entire period of risk associated with the study treatment. The reliability of sexual abstinence needs to be evaluated in relation to the duration of the study and the preferred and usual lifestyle of the participant.)
Notes:
Use should be consistent with local regulations regarding the use of contraceptive methods for participants of clinical studies.
a) Typical use failure rates are higher than perfect-use failure rates (i.e. when used consistently and correctly).
b) If hormonal contraception efficacy is potentially decreased due to interaction with study treatment, condoms must be used in addition to the hormonal contraception during the treatment period and for at least 120 days after the last dose of study treatment.
c) If locally required, in accordance with Clinical Trial Facilitation Group (CTFG) guidelines, acceptable hormonal contraceptives are limited to those which inhibit ovulation.

Pregnancy Testing

WOCBP should only be included after a negative highly sensitive urine or serum pregnancy test.

Pregnancy testing will be performed whenever an expected menstrual cycle is missed or when pregnancy is otherwise suspected.

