Full Ophthalmic Examination (Q8W)		X			X										X			To be performed at screening, Cycle 2 Day 1 and then every 8 weeks (±7 days) from Cycle 2 Day 1 and EOT. An ophthalmic examination at the 30-day follow up is only required if there was a clinically significant abnormality noted at EOT (± 7 days)
Directed Physical Examination			X	X	X	X		X	X	X	X		X					
Height, Weight, and Vital Signs		X	X	X	X	X		X	X	X	X		X		X			Height will be measured at Visit 1 only.
12-Lead Electrocardiogram		X			X			X			X			X	X			ECG will be performed in triplicate to confirm QTc interval at screening. ECG will be performed predose starting at Cycle 2 Day 1.
Echocardiogram/MUGA scan (Q12W)		X			X									X				ECHO/MUGA scans are to be performed at Screening, and pre-dose on Cycle 2 Day 1 and Cycle 5 Day 1, then every 12 weeks and EOT.
ECOG Performance Status			X	X		X		X			X			X				ECOG Performance Status at screening to be assessed within 7 days prior to the first dose of trial treatment.
Post-Study Anticancer Therapy Status															X	X		

Pembrolizumab in Combination with mFOLFOX7 and Binimetinib (Cohort C)

Trial Period:	Screening Phase	Treatment Phase (3-Week Cycles)														End of Treatment	Post- Treatment			Notes		
		End of Treatment																Safety Follow Up	Follow-up Visits	Survival Follow up		
Treatment Cycle/Title	Screening (Visit 1)	1		2		3		4		5 to 35 Discon				Discon	30 days Post last dose	Q9W Post-discon	Q12W					
Treatment Days:		1	8	15	1	8	15	1	8	15	1	8	15	1	8	15	At time of Treatment discon	30 days Post last dose	Q9W Post-discon	Q12W		
Scheduling Window (Days):	-42 to -29	-28 to -1	±3	±3	±3	±3	±3	±3	±3	±3	±3	±3	±3	±3	±3	±3	±3	±3	±7	±7	±14	
Survival Status			<=====X=====>														X	After investigator determined PD or start of new anticancer treatment. In addition, upon Sponsor request, participants may be contacted for survival status at any time during the course of the study.				
Local Laboratory Assessments																						
MSI/MMR Status		X																If tumor testing is obtained by both PCR and IHC, the tumor result should be neither MSI-H by PCR nor dMMR by IHC to identify the non-MSI-H participants.				
Pregnancy Test-Urine or Serum β-HCG		X	X															Pregnancy tests may be performed if clinically warranted, or as defined by local regulations.				
PT/INR and aPTT		X																				
CBC with Differential ^a		X	X	X	X	X	X	X	X	X	X	X	X	X	X	X						
Chemistry Panel ^a		X	X	X	X	X	X	X	X	X	X	X	X	X	X	X						

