3.2.1.2.1 Binimatinib Pre-clinical Studies

Acute, subchronic, chronic and reproductive toxicity, genotoxicity, and phototoxicity studies were completed in rats and monkeys to support the chronic administration of binimatinib to adult patients. There was no evidence of a genotoxic potential in vitro or in vivo. The adverse effects of MEK inhibitors in humans are similar to those observed in rats and monkeys, with the exception of ocular findings. These adverse effects include gastro-intestinal intolerance and diarrhea, rash (skin findings in rats only), retinal events (only seen in humans) and RVO (rarely seen in humans). In vitro and in vivo phototoxicity studies conducted in mice indicate that binimatinib has a low risk of weak phototoxic potential at therapeutic doses. Furthermore, there has been no evidence of phototoxicity or photosensitivity in humans being treated with binimatinib for cancer or for rheumatoid arthritis.

Given the embryo-lethal effects seen in rats and rabbits and the teratogenic effects seen in rabbits, binimatinib should not be used in pregnant women. Women of child-bearing potential must be advised to use highly effective contraception methods.

For further details, please refer to the current binimatinib IB.

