9. Must have been previously treated with fluoropyrimidine, irinotecan, and oxaliplatin.

Note: Adjuvant chemotherapy counts as a first line of prior systemic therapy if there is documented disease progression within 12 months of chemotherapy completion.

Participants for Cohorts B and C

10. Must not have received prior systemic chemotherapy for Stage IV CRC.

Note: Participants who have received adjuvant chemotherapy for non-Stage IV CRC and have documented disease progression within 12 months of chemotherapy completion will not be eligible as these participants may have relative resistance to the proposed 1L regimen, which may undermine the adequate efficacy assessment of this 1L combination.

Participants for Cohorts D and E

11. Must have been previously treated with 1 line of therapy including a fluoropyrimidine plus an oxaliplatin-based regimen.

Note: Adjuvant chemotherapy counts as 1 line of prior systemic therapy if there is documented disease progression within 12 months of chemotherapy completion.

Participants for Cohorts A, C, and E

12. Participants must have a 12-lead ECG and ECHO or MUGA scan performed by the investigator or other qualified person to evaluate cardiac function prior to enrollment in the study. Adequate cardiac function will be assessed by:

- a) LVEF $\geq 50\%$ as determined by MUGA scan or ECHO; and
- b) QT interval calculated according to the Fridericia method (QTcF) value ≤ 480 msec (mean of 3 measurements corrected for heart rate using Fridericia's formula).

Contraception

Male participants:

13. A male participant must agree to use a contraception as detailed in Appendix 5 of this protocol during the treatment period and for at least 180 days, after the last dose of study treatment and refrain from donating sperm during this period.

- a) Male participants with pregnant partners must agree to use a condom.
- b) No additional method of contraception is required for the pregnant partner.

Female participants:

14. A female participant is eligible to participate if she is not pregnant (see Appendix 6), not breastfeeding, and at least one of the following conditions applies:

- a) Not a woman of childbearing potential (WOCBP) as defined in Appendix 6 OR
- b) A WOCBP who agrees to follow the contraceptive guidance in Appendix 6 during the treatment period and for at least 180 days after the last dose of study treatment.

Informed Consent

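### In Cohorts A, C and E a woman of childbearing potential can enter on a single contraceptive method from the lower tier of Table 14, below the highly effective contraception that Section 3.2.1.2.1 says must be advised with binimetinib

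*Combined protocol and SAP*

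**What the plan says.** Section 3.2.1.2.1 gives the reason for caution with binimetinib: "Given the embryo-lethal effects seen in rats and rabbits and the teratogenic effects seen in rabbits". It advises against use in pregnancy and adds: "Women of child-bearing potential must be advised to use highly effective contraception methods".

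The entry rule is in Section 6.1. Criterion 14 applies to every cohort, and option b admits "A WOCBP who agrees to follow the contraceptive guidance in Appendix 6 during the treatment period and for at least 180 days", counted from the end of dosing. It sets no level of effectiveness itself. Appendix 6 (Section 12.6) supplies the standard for women: "Female participants of childbearing potential are eligible to participate if they agree to use one of the contraception methods described in" Table 14.

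Table 14 has three headings. The first, called acceptable, lists condoms and the cap, diaphragm or sponge with spermicide, and is labelled "Failure rate of >1% per year when used consistently and correctly". The other two are both called highly effective, with a failure rate below 1% per year on the same basis.

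For a male participant with a partner of childbearing potential who is not pregnant, Appendix 6 requires either abstinence or the following: "Use a male condom plus partner use of a contraceptive method with a failure rate of <1% per year".

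On testing, Appendix 6 says: "Pregnancy testing will be performed whenever an expected menstrual cycle is missed or when pregnancy is otherwise suspected". The Schedule of Activities note for Cohort C (the same in Cohorts A and E) says: "Pregnancy tests may be performed if clinically warranted, or as defined by local regulations".

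**The concern.** A site decides eligibility from Sections 6.1 and 6.2 and the appendix they cite, not from the background section. A site that follows criterion 14b and Appendix 6 to the letter may enrol a woman into Cohort A, C or E on a condom alone. She would then take, twice daily and for up to about two years, a drug that the protocol says should not be used in pregnancy. She may have been advised to use something better, but if she declines she still qualifies.

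What is at stake is conception while on binimetinib, with possible fetal harm. The statistical results are not at stake: the DLT assessment, the choice of RP2D and the response-rate estimate do not depend on this rule.

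**Working it through.** The plan gives no figure to reproduce and the point needs no calculation. The check is whether the provisions, read together, leave a gap.

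1. **Advice.** Section 3.2.1.2.1 names highly effective methods. Table 14 uses the same term for methods with a failure rate below 1% per year.
2. **Entry minimum.** Criterion 14b requires adherence to Appendix 6, and Appendix 6 requires one Table 14 method. The acceptable heading is part of Table 14 and is labelled above 1% per year.
3. **Comparison.** One label is above 1% and the other below, so the tiers do not overlap. A woman using only a method from the first heading meets criterion 14b but falls short of the advice.
4. **Scope.** Binimetinib is given in Cohorts A, C and E, which is 3 of 5 cohorts.
5. **Other rules in the same appendix.** A non-abstinent man with a non-pregnant partner of childbearing potential needs a condom plus a partner method below 1%. A woman on hormone replacement whose menopausal status is uncertain must use a non-hormonal highly effective method if she wants to continue it. A woman known to be fertile, who takes the drug herself, faces the lowest requirement of the three.
6. **Provisions that might close the gap.**
   - A Table 14 note asks that methods be consistent with local regulations. That can tighten the rule in some countries but sets no minimum across the trial.
   - Table 14 note b adds condoms to hormonal methods when an interaction may weaken them. It does not touch the first heading.
   - Exclusion criterion 27 and Section 9.5.6 require a pregnancy test within 24 hours before the first dose. This excludes an existing pregnancy only.
   - On-treatment tests depend on clinical grounds, local rules, a missed cycle or suspicion. Section 9.5.6 adds monthly testing only where local regulations call for it.
   - Section 8.1 stops treatment after a confirmed positive serum test. This limits exposure after conception.

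None of these raises the contraception level required at entry, so the gap stands.

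**Why no rate is given.** Cumulative failure over t years at a constant yearly rate r is 1 − (1 − r)^t. For the acceptable heading the documents say only that r exceeds 1%, with no upper limit; for the others, only that r is below 1%. A calculation at exactly 1% would describe neither tier, and the difference between tiers cannot be computed. The documents also give no count of women of childbearing potential and no expected choice of method.

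**The case against.** The strongest reply is that nothing here conflicts. Section 3.2.1.2.1 sets a duty to advise and Appendix 6 sets an entry floor; a site can meet both by advising highly effective methods and enrolling on any listed method. This is correct. A reader might infer that the protocol contradicts itself, and the documents do not support that. What remains is a design question: whether advice given for this reason should also be a condition of entry.

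Second, the advice may be delivered firmly elsewhere. Section 3.3 refers participants' risks to the Investigator's Brochures and the consent documents, which are not available here. A reader might infer that women are not properly warned; that cannot be judged. But even firm advice leaves the entry floor where it is.

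Third, the local-regulations note and the pre-dose test are real protections. They are, but the first varies by country and the second acts before treatment starts.

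Fourth, the size of the problem is unknown. This stands in full. It may be tempting to run a 1% yearly rate over an assumed treatment period taken from progression-free survival in other regimens. The result would look precise without measuring either the excess risk or the benefit of the fix.

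**Conclusion.** The concern holds as a gap between the protocol's safety advice and its enforceable minimum in Cohorts A, C and E. It rests on two readings: that Table 14's own labels define highly effective, and that Appendix 6 means what it says in accepting any one listed method.

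Its extent is three of five cohorts. The number of women concerned and the excess failure rate are not derivable. No analysis result changes. The change is still worth making, because the possible harm is serious and the remedy small.

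A reader might also infer that the lower tier is adequate for Cohorts B and D, or that it is inadequate there too. Neither is supported. The documents give this reproductive-toxicity reasoning only for binimetinib and refer chemotherapy background to labelling that is not included, so no statement is made about those cohorts.

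**What to change.** Amend the sentence for female participants in Appendix 6 so that, in Cohorts A, C and E, a woman of childbearing potential must use a method from one of the two highly effective headings of Table 14 for the period set in Section 6.1. Those headings already include the intrauterine device, a vasectomized partner and abstinence, so non-hormonal options remain. Binimetinib-specific eligibility rules already exist (inclusion criterion 12, exclusion criteria 22 and 23), so the restriction fits the protocol's structure.

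The cost is one sentence by amendment, with no new visit or test. The downside is that some candidates for these cohorts must change method before entry.
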